7.3 Premature Withdrawal Criteria

Premature withdrawal of a participant:

- Participants may withdrawal their informed consent at anytime. If gastric sonography has already been performed, anonymous analysis of the previously collected data is eligible.
- Discomfort or pain experienced by the patient at any time of the sonography.
- In case of inability to safely perform the sonography within a maximum of 10 minutes, futher attempts will be stopped and the patient excluded.
- Arising medical or personal information at any time, increasing the urgency of the intervention.

Premature termination of the project:

As this study is designed in a observational, non-interventional methodology, and all patients receive the standard of treatment , no premature termination should occur.

8 Project Measures

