3.2 Categorisation

Category A: collection of health related personal data is associated with minimal risk and burdens only.

Gastric sonography is a very low risk examination. No ionizing radiation is used. Theoretical complications including sensation of local pressure or pain, regional exanthema or allergic reactions to ultrasonic gel will at most be very minor. The complete examination takes approximately five minutes accordingly anaesthesiologic and surgical procedures will not be significantly delayed. Patients and interventions where even a minimal delay may provide a potential health risk are not included in this study.

4 Project Objectives

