4.2 Project Outcomes

Primary Endpoint:

- Correlation of sonographic estimated gastric volume with volume aspirated through a naso- or oro-gastric tube, that was placed by routine.

Secondary Endpoints:

- Performance over time, improvement of examination technique, critical number of examinations to achieve a high quality standard (>80% congruence for estimated and aspirated gastric volume in fluids).
- Association of performance with experience, residents vs. attendings.
- Number of patients classified as empty -> possible implications for management and induction.
- Number of patients with full stomach -> possible implications for management and induction.
- Time used for examinations, time used with growing experience.
- Estimated aspiration risk vs. sonographic gastric volume.
- Total number of pulmonary aspirations.

5 Project Description

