8.1 Measures/procedures to collect health related personal data

At Kantospital Winterthur, a mid-size Swiss teaching hospital all residents and attending anaesthesiologists will receive a structured training in a period of 1 to 8 weeks before inclusion of the first patient. All participating staff will give written informed consent to participate in the study.

To achieve a 90% success rate in correctly recognizing gastric content quality in healthy volunteers, Arzola et al.³⁶ postulated an average number of 24 sonographic examinations to be performed. Based on this and further scientific studies we designed a structured training for all residents and fellows. Primarily, at least 120 minutes of self-study is mandatory for all participants, consisting of scientific background literature, a step for step guide and educational videos. This is followed by a hands-on course, split into a 30 minute lecture and theoretic background introduction and 120 minutes supervised practical training on healthy volunteers. Group sizes per ultrasound machine and tutor/expert will range from 2 to 3 participants. First training objective is a successful differentiation of gastric content into empty, fluid, solid or mixed. An empty stomach seems the hardest quality to sonographically visualise,³⁶ therefore a special effort will be made on identifying this quality. The next objective is the identification and localization of the antral cross-sectional area in a supine and right lateral decubitus (RLD) position in the case that fluid gastric content is present. Every participant will perform at least 20 examinations during this hands-on course with a direct expert feedback.

Further, all participants will continue to train their sonographic skills on healthy volunteers and team members at our institution. Before including the first patient all the examiners will be tested by a tutor/expert and received their approval. In the first month of recruitment, new sonographers will be supervised by our tutor/expert team whenever possible. Individual feedback and support if needed should be available any time.

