Tutors/experts are all expert sonographers on different modalities. They will receive a preceding 240 minutes training, consisting of a 60 minutes theoretic introduction and a 60 minutes course by a radiologist and abdominal sonography expert, certified by the Swiss Society for Sonography. The remaining time will consist of individual exercise on healthy volunteers and at least 10 trial sonographies with gastric volume calculation under supervision of another member of the tutor group.

Our study will be performed mainly in the induction rooms of our operating unit and occasionally inside the operating theatre. Standard care will be given to every patient at the usual location, with our usual equipment (anaesthetic machine, monitoring, medication and airway devices and so on) and by our usual anaesthesiologic team members. Sonographic examination and determination of the gastric content will be executed on one of our standard ultrasound machines (Venue and LOQIC e from GE-Healthcare®) with a curved array low frequency (2-10 Hz) abdominal probe or our portable ultrasound devices (IQ+ from Butterfly Network Inc.®).

Before performing the sonographic examination, the responsible anaesthesiologist will be asked to rate the estimated risk of pulmonary aspiration, based on personal impression, patient history and clinical finding. All anaesthetists are advised to perform the examination only if they could guarantee privacy before they expose patient abdomen for the examination. Primarily, a qualitative assessment of the gastric content should be performed in supine and right-lateral decubitus (RLD) position. In low volume states a right-lateral decubitus position (RLD) has the advantage of a gravitational shift to the antrum. That is why we plan to perform the examination in both positions. If RLD position is not possible due to patient factors a half sitting position can be tried. Gastric content will be classified into empty, fluid, solid or mixed. Examiners will be asked to classify sonographic conditions into poor, medium or good and provide a reason in case of limited conditions. If fluid gastric content is detected an estimation of the quantity should be performed as follows.

After identification, CSA will be measured and gastric content is estimated by implementation of the formula described by Perlas et al: ^{20, 28}

$$\text{Gastric Volume (ml)} = 27.0 + 14.6 \times \text{right-lateral CSA (cm}^2\text{)} - 1.28 \times \text{age (years)}.$$

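### Section 7.3 excludes patients whose scan is not achieved within 10 minutes and nothing keeps the attempt, so the secondary endpoint on examination time is cut off at 10 minutes

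*Protocol*

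**What the plan says.** Section 7.3 lists, among the reasons for premature withdrawal of a participant: "In case of inability to safely perform the sonography within a maximum of 10 minutes, futher attempts will be stopped and the patient excluded". The only sentence there that keeps data after withdrawal concerns patients who withdraw consent once the scan has been done. It does not mention the 10-minute stop.

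Section 4.2 makes examination time a secondary endpoint: "Time used for examinations, time used with growing experience". Section 11.2 repeats it. Section 3.2 gives the expected duration: "The complete examination takes approximately five minutes". No standard deviation and no expected share of time-outs appear anywhere.

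Some data items could hold a stopped scan. Section 11.2 lists the examination time and the reason a scan was not done. Section 8.1 provides a data sheet for the sonography and a grading of conditions: "Examiners will be asked to classify sonographic conditions into poor, medium or good and provide a reason in case of limited conditions". None of these is tied to a scan stopped at 10 minutes.

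**The concern.** The rule removes an enrolled, consented patient because of how the examination under study turned out, and the criterion is the variable that section 4.2 sets out to measure. The slowest attempts leave the data by design, so the remaining times describe completed scans and not the time that scanning takes in this department.

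The learning question suffers as well. The aim is to validate a training programme. If slow or failed scans cluster early in an operator's series, excluding them makes the early period look faster than it was, and the improvement appears smaller.

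A later analysis plan can repair this only if the attempt was recorded. An examiner who reads "In case of inability to safely perform the sonography within a maximum of 10 minutes, futher attempts will be stopped and the patient excluded" as the end of the case may enter nothing, and the elapsed time is then lost.

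**Working it through.** **1. Reading the text.** Three things would have to be stated for the attempt to survive: that it is recorded, that its time is kept, and that it enters an analysis. Section 7.3 states exclusion. Section 8.1 provides a sheet for sonography data, without mention of stopped scans. Section 11.2 lists the time and reason fields, without linking them to a stop. None of the three is stated.

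**2. Counts.** Section 11.1 expects 30 residents and 20 attendings, hence 50 operators, with 30 to 40 examinations each. 50 × 30 = 1500 and 50 × 40 = 2000, which reproduces the protocol's target of 1500 to 2000. These totals serve below as the number of attempts.

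**3. Size, under assumptions.** From the protocol: the cut-off of 10 minutes, and about five minutes as the typical duration, taken here as a median m. Assumed: log-normal times, with log-SD s from 0.2 to 0.5.

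- z = ln(10/m)/s; share stopped f = 1 − Φ(z)
- mean of completed scans = m·exp(s²/2)·Φ(z − s)/Φ(z)
- mean with stopped scans entered at 10 = (1 − f) × mean of completed + 10f
- median of completed scans = exp(ln m + s·Φ⁻¹(0.5(1 − f)))

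Example, m = 5 and s = 0.4: z = 0.693/0.4 = 1.733, f = 4.16%, mean of completed 5.135. With stops at 10 minutes: 0.9584 × 5.135 + 10 × 0.0416 = 5.338. The shortfall is 0.202 minutes.

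| s | f | stopped of 1500–2000 | mean, completed | mean, stops at 10 | shortfall (min) | median, completed |
|---|---|---|---|---|---|---|
| 0.2 | 0.03% | 0.4–0.5 | 5.100 | 5.101 | 0.001 | 5.000 |
| 0.3 | 1.04% | 15.6–20.9 | 5.168 | 5.218 | 0.050 | 4.980 |
| 0.4 | 4.16% | 62.3–83.1 | 5.135 | 5.338 | 0.202 | 4.897 |
| 0.5 | 8.28% | 124.2–165.7 | 5.018 | 5.430 | 0.413 | 4.747 |

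At s = 0.5 this is 124.2/50 = 2.5 to 165.7/50 = 3.3 stopped scans per operator. The shortfall compares completed scans with stopped scans entered at 10 minutes. It does not guess how long they would have run. Censoring at 10 minutes recovers the median of 5.00.

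**4. Gain with experience, illustration.** Assume that the median falls from 6 to 4 minutes, a true gain of 2.00.

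| s | f at m = 6 | f at m = 4 | median gain, completed scans |
|---|---|---|---|
| 0.3 | 4.43% | 0.11% | 5.901 − 3.998 = 1.90 |
| 0.4 | 10.08% | 1.10% | 5.704 − 3.978 = 1.73 |
| 0.5 | 15.35% | 3.34% | 5.447 − 3.917 = 1.53 |

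**5. What the rule does not reach.** The primary endpoint correlates an estimated with an aspirated volume, and the quality standard is "critical number of examinations to achieve a high quality standard (>80% congruence for estimated and aspirated gastric volume in fluids". Both need an estimated volume, which a scan that was not achieved does not supply.

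**The case against.** **Exclusion need not mean deletion.** The sentence stands under premature withdrawal and ends participation; it does not say that recorded data are discarded. A time-out leaves consent intact, so the silence of the retention sentence is weak evidence of deletion. This stands in part: the protocol does not order deletion. But it states exclusion and nowhere says that the attempt is kept. If the sponsor means exclusion from the volume comparison only, the text should say so.

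**Time-outs may be very rare.** Section 8.1 requires training and a test: "Before including the first patient all the examiners will be tested by a tutor/expert and received their approval". Sections 3.1 and 5.4 speak of a few minutes. This stands. With a median of 4 minutes the model gives f of 0.1%, 1.1% or 3.3% at s = 0.3, 0.4 or 0.5. With no time-outs there is no bias.

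**The log-normal tail does not describe every stop.** The rule covers scans that cannot be done safely as well as slow ones, and a stop may come before 10 minutes. Such scans need not have a completion time at all. This stands, and it shapes the fix: elapsed time must be the actual stop time, and safety stops must be shown apart.

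**Censoring and tables belong in an analysis plan.** As a matter of detail, yes. The exclusion, however, is fixed in the protocol, and an analysis plan cannot restore an attempt that was never recorded.

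**A stronger reading to avoid.** A reader might infer that the success analyses in section 11.2, or the comparison in "Association of performance with experience, residents vs. attendings", are inflated because failed scans drop out of the denominator. The protocol does not define success and names no rate over all attempts; its one stated standard needs a completed scan. The inference holds only if success is meant to cover all attempts, which is not stated.

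**Conclusion.** The point holds for the examination-time endpoint. Following section 7.3 as written restricts analysed times to scans achieved within 10 minutes. The direction is clear: if any scans are stopped, reported time is too low, and if stops are commoner early, the gain with experience is too small.

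The size cannot be taken from the protocol. Under the assumed log-normal times with median 5 minutes and log-SD 0.2 to 0.5, the mean is low by between practically nothing and 0.41 minutes (about 25 seconds). The illustrated gain of 2.00 minutes appears as 1.53 to 1.90 at log-SD 0.5 to 0.3. The spread, the fall from 6 to 4 minutes and the shape of the distribution are all assumptions.

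It would be wrong to conclude that the primary correlation, or the critical number of examinations as defined by congruence in fluids, is directly biased by this rule. Severity is minor to moderate and confined to a secondary endpoint; the reason to act is that unrecorded attempts cannot be recovered.

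**What to change.** Leave the 10-minute stop unchanged.

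- **Section 7.3:** replace the closing words on exclusion. The new wording should say that the scan is stopped, that the attempt is kept and recorded as not achieved with its elapsed time and reason, and that it is left out of the volume-agreement analyses only.
- **Section 11.2:** treat the time of a stopped scan as censored at its actual stop time, which is 10 minutes for a time-out. Report stops for safety or discomfort separately. Give the number and reasons of stopped scans by sonographer experience and examination order.
- **If success is meant to cover all attempts,** section 11.2 should say so; stopped scans then belong in the denominator.

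The cost is one sentence in section 7.3, about two in section 11.2, one more entry per stopped scan and slightly more analysis. The scan procedure does not change. A recorded reason is enough; examiners need not judge whether they or the patient caused the stop.

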8.1 Measures/procedures to collect health related personal data

At Kantospital Winterthur, a mid-size Swiss teaching hospital all residents and attending anaesthesiologists will receive a structured training in a period of 1 to 8 weeks before inclusion of the first patient. All participating staff will give written informed consent to participate in the study.

To achieve a 90% success rate in correctly recognizing gastric content quality in healthy volunteers, Arzola et al.³⁶ postulated an average number of 24 sonographic examinations to be performed. Based on this and further scientific studies we designed a structured training for all residents and fellows. Primarily, at least 120 minutes of self-study is mandatory for all participants, consisting of scientific background literature, a step for step guide and educational videos. This is followed by a hands-on course, split into a 30 minute lecture and theoretic background introduction and 120 minutes supervised practical training on healthy volunteers. Group sizes per ultrasound machine and tutor/expert will range from 2 to 3 participants. First training objective is a successful differentiation of gastric content into empty, fluid, solid or mixed. An empty stomach seems the hardest quality to sonographically visualise,³⁶ therefore a special effort will be made on identifying this quality. The next objective is the identification and localization of the antral cross-sectional area in a supine and right lateral decubitus (RLD) position in the case that fluid gastric content is present. Every participant will perform at least 20 examinations during this hands-on course with a direct expert feedback.

Further, all participants will continue to train their sonographic skills on healthy volunteers and team members at our institution. Before including the first patient all the examiners will be tested by a tutor/expert and received their approval. In the first month of recruitment, new sonographers will be supervised by our tutor/expert team whenever possible. Individual feedback and support if needed should be available any time.

Tutors/experts are all expert sonographers on different modalities. They will receive a preceding 240 minutes training, consisting of a 60 minutes theoretic introduction and a 60 minutes course by a radiologist and abdominal sonography expert, certified by the Swiss Society for Sonography. The remaining time will consist of individual exercise on healthy volunteers and at least 10 trial sonographies with gastric volume calculation under supervision of another member of the tutor group.

Our study will be performed mainly in the induction rooms of our operating unit and occasionally inside the operating theatre. Standard care will be given to every patient at the usual location, with our usual equipment (anaesthetic machine, monitoring, medication and airway devices and so on) and by our usual anaesthesiologic team members. Sonographic examination and determination of the gastric content will be executed on one of our standard ultrasound machines (Venue and LOQIC e from GE-Healthcare®) with a curved array low frequency (2-10 Hz) abdominal probe or our portable ultrasound devices (IQ+ from Butterfly Network Inc.®).

Before performing the sonographic examination, the responsible anaesthesiologist will be asked to rate the estimated risk of pulmonary aspiration, based on personal impression, patient history and clinical finding. All anaesthetists are advised to perform the examination only if they could guarantee privacy before they expose patient abdomen for the examination. Primarily, a qualitative assessment of the gastric content should be performed in supine and right-lateral decubitus (RLD) position. In low volume states a right-lateral decubitus position (RLD) has the advantage of a gravitational shift to the antrum. That is why we plan to perform the examination in both positions. If RLD position is not possible due to patient factors a half sitting position can be tried. Gastric content will be classified into empty, fluid, solid or mixed. Examiners will be asked to classify sonographic conditions into poor, medium or good and provide a reason in case of limited conditions. If fluid gastric content is detected an estimation of the quantity should be performed as follows.

After identification, CSA will be measured and gastric content is estimated by implementation of the formula described by Perlas et al: ^{20, 28}

$$\text{Gastric Volume (ml)} = 27.0 + 14.6 \times \text{right-lateral CSA (cm}^2\text{)} - 1.28 \times \text{age (years)}.$$

This model is based on gastroscopic fluid assessment and highly validated by several publications. ²⁸

After placement of the routine naso- or orogastric tube, which is a standard procedure for both RSIs and advanced laryngeal masks at our institution - we compare the calculated and effective suctioned volume of the gastric content and analyse the difference and quality of the sonographic measurement. In some patients a gastric tube is contraindicated or not possible to place correctly. In this case an exclusion of the study is mandatory according to our exclusion criteria. Patients planned for an intervention in a regional anaesthesia will not receive a gastric tube.

In exceptional cases the responsible anaesthesiologist is allowed to upgrade patients from an advanced laryngeal mask to an RSI after ultrasound performance to ensure patient safety. Downgrading from RSI to advanced laryngeal masks on base of the ultrasound results is not allowed.

All data concerning the sonography will be noted in a password protected Excel sheet only available to institute members by the responsible anaesthesiologist performing the examination. Background patient data including demographic data are collected during the structured preoperative anaesthesiologic assessment according to in house standard procedures and data management. Data will be coded and condensed in a password-protected Excel File, only accessible to study personnel. A patient identification log will be kept in a locked archive for data verification processes only. To guarantee seamless traceability we will create a immutable PDF file after all relevant changes or at least once per month and store it in a separate study folder only accessible to study personnel. An additional hard copy will be created and printed once per month and stored in a locker in our administrative office.

9 Safety

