4.1 Project Objectives

Primary objectives:

- Establish preoperative gastric sonography in patients with risk factors for pulmonary aspiration at the Kantonsspital Winterthur, Department of Anaesthesiology through a structured training/education - validated by comparing sonographic estimated and directly measured gastric content.

Secondary objectives:

- Identify possible confounders and variables in individual training.
- Emphasize the importance and effectiveness of this diagnostic tool to improve anaesthesiologic management and possibly patient safety by identifying the number of possible interventions and changes in anaesthesiologic management and correlation of estimated and actual gastric volume in fluids.

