5.2 Number of Project Participants

We aim to include at least 500 up to 2200 patients. For further informations see below.

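### Volume is estimated only for scans read as fluid, and no stated endpoint explicitly checks an empty reading against the aspirate

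*Protocol*

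**What the plan says.** The scan rule is in Protocol section 8.1. After classification into four classes, the antral area (CSA) and the volume formula follow a condition: "If fluid gastric content is detected an estimation of the quantity should be performed as follows". No section assigns an empty scan a value such as 0 ml or asks for its CSA.

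Once the gastric tube is in place, section 8.1 states: "we compare the calculated and effective suctioned volume of the gastric content and analyse the difference and quality of the sonographic measurement". The tube is routine for RSI and laryngeal mask patients. Regional anaesthesia patients do not get one. Section 11.2 lists the effective quantity of gastric content as a collected variable, with no restriction by scan class.

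The aims and endpoints are worded as follows:

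- Primary objective (section 4.1): the training is to be "validated by comparing sonographic estimated and directly measured gastric content".
- Secondary objective (section 4.1): it includes "correlation of estimated and actual gastric volume in fluids".
- Primary endpoint (sections 4.2 and 11.2): the correlation of estimated with aspirated volume, with no stated limit to fluids.
- Quality standard, a secondary endpoint (section 4.2): "critical number of examinations to achieve a high quality standard (>80% congruence for estimated and aspirated gastric volume in fluids").
- The only endpoint that names the empty class (section 4.2): "Number of patients classified as empty -> possible implications for management and induction".

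Section 8.1 also remarks: "An empty stomach seems the hardest quality to sonographically visualise".

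**The concern.** Whether a patient has an estimated volume depends on the scan's own reading. If the scan misses fluid and reads empty, there is no calculated volume to set against the suctioned one, so the error does not appear in a comparison of the two.

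This matters because the primary objective speaks of gastric content as a whole, and because an empty reading is the one that could later support a change in induction practice. The protocol counts such readings and links the count to management, but it does not say how often they are right. A high correlation among fluid-read scans could then be taken as validation of the whole examination.

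**Working it through.** **Which patients enter which result, as written**

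| True content, scan reading | Calculated volume prescribed | In the 80% standard | In the primary correlation | Aspirate (if tubed) |
|---|---|---|---|---|
| Fluid, read fluid | yes | yes | yes | yes |
| Fluid, read empty | no | no | no, by inference | yes |
| Empty, read empty | no | no | no, by inference | yes |

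The entries for the 80% standard follow from its limit to fluids and from the missing volume. Those for the primary correlation are inferred from section 8.1, which compares the calculated with the suctioned volume.

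**Data available for a check of the empty class**

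Section 11.1 gives 2718 − 275 − 204 = 2239 eligible RSI and about 1000 mask or regional patients. The tubed share is 2239/3239 = 69% if all 1000 are regional, and 100% if all are masks. The protocol gives no share of empty readings, so I assume 30% to 50%. Section 5.2 sets the lowest target ("We aim to include at least 500 up to 2200 patients"); section 11.1 starts from 1500.

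- 500 enrolled: 500 × 0.691 × 0.30 = 104, up to 500 × 0.50 = 250 empty scans with an aspirate.
- 1500 enrolled: 1500 × 0.691 × 0.30 = 311, up to 1500 × 0.50 = 750.

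If none of these exceeded 1.5 ml/kg (the cut-off in section 3.1), the exact upper 95% limit is 1 − 0.025^(1/n):

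| n | 104 | 250 | 311 | 750 |
|---|---|---|---|---|
| Upper limit | 3.5% | 1.5% | 1.2% | 0.5% |

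The check would therefore be informative even at the lowest target. If up to 5% exceeded the cut-off, that would be up to 13 patients (5% of 250 = 12.5) or 38 (5% of 750 = 37.5).

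**Does the fluid-only correlation show misreading?**

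This is a simulation of 400,000 stomachs, and every input is my assumption:

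- fluid volume gamma with shape 2 and scale 60 ml; empty volume gamma with shape 1 and scale 8 ml;
- estimate = volume + normal error with SD 45 ml, floored at 0;
- cut-off 1.5 ml/kg × 75 kg = 112.5 ml;
- 30% or 50% of stomachs fluid-filled.

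An empty reading counts as test-negative. Each range covers the two fluid shares. In the last three rows the chance of misreading falls with volume along a logistic curve.

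| Fluid stomachs read as empty | Fluid-only r | Sensitivity for >1.5 ml/kg | Empty scans above cut-off |
|---|---|---|---|
| 0% | 0.89 | 0.85 | 0% |
| 20%, independent of volume | 0.89 | 0.67–0.68 | 3.5–7.4% |
| 20%, falling with volume (scale 60 ml) | 0.89 | 0.79–0.80 | 1.2–2.4% |
| 20%, falling with volume (scale 30 ml) | 0.89 | 0.83 | 0.4–0.7% |
| 20%, falling with volume (scale 15 ml) | 0.88 | 0.84–0.85 | under 0.1% |

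The correlation barely moves between a negligible and a serious failure of the empty class. Entering empty scans as 0 ml would change that: r over empty and fluid scans is 0.94 to 0.95 with no misreading, 0.80 to 0.83 with 20% independent misreading, and 0.91 to 0.95 when misreading falls with volume. The coding of empty scans therefore matters to the primary result.

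**The case against.** Five points can be made on the other side.

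1. **The primary endpoint is not limited to fluids.** The restriction sits in the secondary congruence standard and in a secondary objective, and nothing forbids entering an empty scan as 0 ml. This stands. Exclusion from the primary correlation is the natural reading of section 8.1, not a stated rule.
2. **The success analyses may already cover class accuracy.** In section 8.1 the quality of content means the four classes, and the success rate cited from the learning-curve study is for recognising them. Logistic regression and cumulative sum curves suit a right-or-wrong outcome. This is a plausible reading, but section 11.2 does not define success or mention the empty class.
3. **A statistical analysis plan, not shown here, could add the table.** It could, since the data exist. But the fluid-only trigger and the fluid-only quality standard are fixed in the protocol, alongside an objective about content in general. That mismatch is more than a detail left for later.
4. **Estimating only where fluid is seen is defensible.** The printed formula turns negative for small antra: at age 70 below (1.28 × 70 − 27)/14.6 = 4.3 cm². I accept this, and the fix does not ask for a CSA in empty scans.
5. **Misses may be mostly trace volumes.** Scanning in two positions and extra training on the empty class both work against larger misses. This also stands, and it is why no size is claimed.

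**Conclusion.** The point holds as a gap in what the stated endpoints verify. False-empty readings are outside the 80% standard and, on the natural reading, outside the primary correlation. No stated endpoint explicitly tests the empty class against an aspirate that is collected anyway in RSI and laryngeal mask patients.

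The size is unknown. The documents give no class shares and no misreading rates. On the assumptions above, with 20% of fluid stomachs misread, between under 0.1% and 7.4% of empty scans would exceed the cut-off, and the fluid-only correlation would not show which.

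A reader might infer more than this, and three stronger readings are not supported:

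- That the protocol expressly bars empty scans from the primary correlation. It does not say so.
- That the reported correlation will be biased upwards. The simulated fluid-only value hardly changes, and no direction is claimed.
- That participants are put at risk. Section 8.1 does not allow a downgrade from RSI on the scan result, so the issue is what may be concluded.

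Severity is minor to moderate: a cheap improvement that lets the study answer its own question.

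**What to change.** Add to section 11.2 (or the analysis plan), and align section 4.2:

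1. In all tubed patients, tabulate aspirated volume by sonographic class (empty, fluid, solid, mixed).
2. Report, with 95% CI, the proportion of empty scans whose aspirate exceeds 1.5 ml/kg. Also report sensitivity and specificity for that cut-off over empty and fluid scans, with empty counted as test-negative.
3. Describe the volume correlation and the congruence result as applying to fluid-read, tubed patients, not as validation of the whole examination.

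Scan class, aspirate and weight are already collected, so the cost is wording and a little more analysis. The downside is that the validation result may look less favourable.
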